Recruitment: Subjects will be recruited from the physician clinics at GWU, Medical Faculty Associates, where [name] is a clinician, as well as through referral from the VA. All patients will receive counseling regarding the study aims and methods.

Study Design Overview: We propose a 2-arm randomized, double-masked, placebo-controlled, parallel group, longitudinal study of 12-weeks duration. (See study design below), recruited over 3 years. The 12 week time interval has been previously shown adequate to observe changes in endothelial progenitor stem cells, biochemistry and importantly, PWV changes [20, 36]. Patients will be randomized to 2 groups:

Control, (n=20), Insulin/Metformin/Both + Lifestyle + Placebo

Treatment, (n=20) Insulin/Metformin/Both + Lifestyle + Linagliptin 5mg

This proposed study is based on patients with type 2 diabetes of ≤ 15 years duration, who are on stable dose of insulin, Metformin, or both for at least 3 months but still remain poorly controlled with HbA1C between 6.5% and 10% (both inclusive), but not overtly out of control ($> 10\%$ of HbA1C). Our study design is similar to that of Fadini et al [20] where Sitagliptin was compared to placebo with endothelial progenitor cells as an outcome measure in patients with type 2 diabetes over 4 weeks.

Though our study is over 12 weeks we do not anticipate significant drop in HbA1C in between the two groups in this relatively short time period to act as a confounding factor on CD34+ cell number, function and gene expression.

Most clinical studies looking at HbA1C reduction were of a much longer duration of 6 months or above and most DPP-4 inhibitor studies are with animal EPCs where comparison with human CD34+ population is difficult to make. In one study (58) where saxagliptin was used for **12 weeks** in drug-naïve type 2 diabetes patients there was placebo-subtracted HbA1c reduction noted of 0.45-0.63%. It showed mean placebo-subtracted reductions in fasting serum glucose of 20 mg/dL. From our laboratory studies of in vitro human EPC studies we do not think glucose level change of 20 mg/dL is significant enough to account for changes in EPC number, function and gene expression. However we will take the possibility of glycemia change/ reduction in experimental arm into account during statistical analysis of the results between the Linagliptin and placebo groups.

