The distributional assumptions of all measures will be examined. Means and standard deviations will be computed for continuous measures and proportions for categorical variables. Graphical representations of the mean group slopes and individual slopes will be generated and inspected. Study groups will be compared to determine whether any imbalance between the groups on patient characteristics remain after randomization. If imbalance is evident, by inspection, all models will be adjusted for the unbalanced covariates. Change in outcome over time will be examined using a multilevel approach with linear mixed models (LMM) (53, 54). The longitudinal multilevel modeling approach will enable us to examine characteristics of within-person change, as well as between-group differences that may influence change. LMMs handle missing data more efficiently than traditional ANOVA designs. In the linear mixed models, the patient is considered a random effect and the outcome measured at specific time points is nested within patient. In an initial model containing only the variable TIME, we will use a likelihood ratio test to determine whether a random effect for time should be modeled.

The model below represents a random intercept for patient and a random coefficient for TIME.

$$Y_{ij} = \beta_0 + \beta_1 Time_{ij} + u_{i0} + u_{i1} Time_{ij} + \varepsilon_{ij}$$

We will examine whether TIME may be modeled linearly by testing the added contribution of TIME (represented with two indicator variables) to a model with TIME as a single continuous variable. Assuming time may be modeled as a continuous variable, subsequent analyses will add study group and other patient characteristics as covariates. We are particularly interested in whether there is a significant interaction between study group and time, adjusting for other patient level covariates. A significant interaction would indicate that the slopes in outcome over time differ by study group. If the global test of interaction is significant, subsequent significance testing of the pairwise comparisons of group slopes group will be adjusted for multiple comparisons. The model also includes coefficients for the group-by-time interactions and random effects for patient and time.

$$Y_{ij} = \beta_0 + \beta_1 Time_{ij} + \beta_2 Group_i + \beta_3 (Time_{ij} \times Group_i) + u_{i0} + u_{i1} Time_{ij} + \varepsilon_{ij}$$

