In the event that TIME is modeled using indicator variables, two indicator variables will be used to represent the three time points, with baseline serving as the reference category. The interaction between GROUP and TIME will be modeled in a similar fashion using two additional indicator variables. The above multivariable model enables us to adjust for time-varying covariates, such as glucose. Since glucose will be measured contemporaneously with the outcomes at each visit, however, causal interpretations of glucose and any outcome are suspect. As such, we will consider glucose as a nuisance covariate, and consider any relationship between glucose and an outcome as merely associative.

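### The plan treats on-treatment glucose as a covariate but never says whether the main Linagliptin–placebo estimate includes it; including it shifts that estimate if glucose is related to the outcome and also differs between arms

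*Combined protocol and SAP*

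**What the plan says.** Three places in the combined protocol and SAP bear on how glucose enters the arm comparison.

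- **Study Design Overview (within section 4.5).** After discussing another gliptin, the investigators write that "we will take the possibility of glycemia change/ reduction in experimental arm into account during statistical analysis of the results". No model is named. The same paragraphs say that they expect no significant HbA1c difference between the groups over 12 weeks, and that they doubt a 20 mg/dL glucose change is enough to explain changes in the cells.
- **Data Analysis (section 5), main model.** The key test is the group-by-time interaction: "We are particularly interested in whether there is a significant interaction between study group and time, adjusting for other patient level covariates". The covariates are not listed, and the displayed equation has time, group, their product and random effects, but no glucose.
- **Data Analysis, last paragraph.** "The above multivariable model enables us to adjust for time-varying covariates, such as glucose". Because glucose is measured at the same visits as the outcomes, the plan says "causal interpretations of glucose and any outcome are suspect" and concludes: "As such, we will consider glucose as a nuisance covariate".

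The objectives (Synopsis and section 2.1) ask for the effect of adding Linagliptin. The hypotheses (Synopsis and section 1) go further and propose a benefit beyond glucose control and independent of HbA1c reduction.

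**The concern.** Glucose at weeks 6 and 12 is measured after randomisation, and section 1 gives the drug's indication as improving glycaemic control. Treating a variable as a nuisance is safe when it is a baseline characteristic. It is not safe for one that treatment may change, because conditioning on it can remove part of the drug's effect or bring in association from other causes.

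The plan's caution covers only the causal reading of the glucose coefficient. It does not say what adjustment does to the group-by-time term, which is the term the trial is about. One analyst could fit the displayed equation and another could add glucose as the closing paragraph says. Both would be following the plan, they could report different Linagliptin effects from the same data, and no rule says which is the trial result. Section 4.4 allows the clinical outcomes to be unblinded before the cellular data have been analysed, which is a further reason to settle the model beforehand.

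**Working it through.** **Inputs from the plan (section 5):** SD 15 cells, visit correlation 0.60, weeks 0/6/12, slope difference 1 cell/week (12 cells at week 12), 18 completers per arm. **From Study Design Overview**, for a different gliptin in drug-naive patients: "It showed mean placebo-subtracted reductions in fasting serum glucose of 20 mg/dL". (The reference number given there points, in the reference list, to a paper on energy expenditure.) **Assumed, because the documents give neither:** glucose SD 30 to 50 mg/dL; glucose–cell correlation r from -0.4 to +0.4, the same between and within patients; glucose visit correlation 0.6.

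**1. The plan's own figure.** The sum of squares of time about its mean is 36 + 0 + 36 = 72.

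Slope SE = √[2 × 15² × (1 − 0.60) / (18 × 72)] = √(180/1296) = 0.373 per week, or 4.47 cells at week 12.

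1/0.373 = 2.683, and 2.683 − 1.645 = 1.038, so power is 0.85 against the stated 0.84. The match needs a one-sided 0.05 test; a two-sided test gives 0.765. The plan does not state sidedness. That is a separate matter and does not affect this point.

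**2. Shift from adjusting for glucose.** Let b be the glucose coefficient and F the week-12 fall in glucose on Linagliptin relative to placebo.

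b = r × 15 / SD of glucose; adjusted estimate = 12 + b × F.

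| Glucose SD | F (mg/dL) | Shift (cells) | Estimate, r = -0.4 to +0.4 |
|---|---|---|---|
| 30 | 20 | 10r | 8 to 16 |
| 50 | 20 | 6r | 9.6 to 14.4 |
| 30 | 10 | 5r | 10 to 14 |
| 50 | 10 | 3r | 10.8 to 13.2 |
| any | 0 | 0 | 12 |

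At r = 0 the estimate is 12 in every row. Very large simulated samples (SD 30, F = 20, random intercept) gave 8.06, 10.07, 11.91, 14.07 and 15.98 at r = -0.4, -0.2, 0, +0.2 and +0.4. If a correlation of 0.4 in size exists only between patients, the expected range narrows to 10.85–13.15; if only within patients, it is 8.94–15.06.

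**3. At trial size.** In a separate simulation with 18 per arm, assumed glucose SD 40 and F = 20, r of -0.1, -0.3 and -0.5 gave about 11.2, 9.7 and 8.3 cells. Two-sided power fell from about 0.77 to 0.70, 0.61 and 0.56. With no true drug effect and glucose linked to the cells only through a common cause, the adjusted model averaged -2.3 cells (r = -0.3) or -3.8 cells (r = -0.5). It rejected in 8% or 17% of trials, against about 5% unadjusted. With no arm difference in glucose there was no shift at any r.

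**4. The adjusted term need not be the glycaemia-independent effect either.** Suppose glucose has no causal effect, the true direct effect is 12, and an unmeasured cause loads 0.3 or 0.5 on both variables. With SD 30 and F = 20 the adjusted estimate is 11.1 or 9.5 if the cause moves glucose and cells in opposite directions, and 12.9 or 14.5 if in the same direction.

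**5. Optional precision gain.** The displayed model leaves the week-0 arm difference free, although week 0 precedes dosing. With a random intercept only, the variance of the week-12 difference, in units of σ²/n, is:

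- free week-0 difference: 4(1 − 0.60) = 1.600, SE = √(1.600 × 225/18) = 4.47;
- common week-0 mean with visit indicators: 2(1 − 0.60²) = 1.280, SE 4.00, a 20% reduction.

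The plan tests for a random slope ("we will use a likelihood ratio test to determine whether a random effect for time should be modeled"). If one is kept, the gain depends on its SD and on the intercept–slope correlation. Over the settings tried it ran from about 25% to 0.02%, and at zero correlation it fell from 19.1% to 4.8% as the slope SD grew from 0.2 to 1.6 baseline SDs over 12 weeks.

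Visit indicators matter for this option. With a common baseline and linear time, a true 12-cell week-12 difference is estimated as 12.86 if the effect is complete by week 6, and as 11.14 if it is absent until after week 6. With indicators both give 12.00.

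**The case against.** The strongest reply is that the plan has thought about this. Study Design Overview expects no significant HbA1c difference and doubts that 20 mg/dL matters for the cells, so both links needed for a shift are expected to be weak. This stands as a limit on size. It does not settle the ambiguity, because the same paragraph still promises to account for glycaemia.

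Second, the displayed equation has no glucose, patient-level covariates would normally be fixed per patient, and the closing paragraph says only that the model permits adjustment. A natural reading is that the displayed model is primary. That is fair, but the sentence assigning glucose a nuisance role is not permissive, and no text ranks the two fits.

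Third, the investigators want a glycaemia-independent effect. That is a legitimate question, and some shared causes are limited or recorded: lifestyle advice goes to both arms, accelerometers record activity, and insulin titration is tied to HbA1c above 10%. But neither activity nor insulin dose is placed in the model.

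Fourth, this is a pilot, the sizes above rest on assumed inputs, and even the largest tabulated shift (4 cells) is below one standard error. All true. The plan nevertheless applies a 0.05 significance threshold.

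Three stronger readings are tempting and unsupported. A reader might infer that any glucose–cell relation biases the adjusted estimate; it does not unless the arms also differ in glucose. A reader might infer that the plan commits to a glucose-adjusted primary result; it commits to neither fit. A reader might infer that the free week-0 difference is a mistake; it is conventional, causes no bias and makes no stated power wrong.

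**Conclusion.** The point holds as a conditional one. The plan gives on-treatment glucose a covariate role without saying whether the main group-by-time estimate contains it. If glucose is related to the cells and the arms differ in glucose, the adjusted estimate departs from the randomised effect that the objectives ask for, by coefficient times arm difference. If either condition fails, both fits target the same effect.

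The documents give no glucose SD, no glucose–cell correlation and no glucose effect for Linagliptin itself, so neither the size nor the direction of a shift can be established. The 8-to-16-cell range is an illustration that rests on the assumed SD, the assumed correlations and another drug's 20 mg/dL. On the investigators' own expectations the real shift may be small. The clarification is still worth making before unblinding, because it concerns which number is the trial's result. The common week-0 mean is a separate efficiency option.

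**What to change.** **Main change.** State in Data Analysis that the primary Linagliptin–placebo estimate comes from the mixed model with no post-baseline covariate; week-0 glucose may be included. Report the model with glucose at weeks 6 and 12 as a labelled supportive, non-causal analysis for the glycaemia-independent hypothesis, and bring the sentence in Study Design Overview into line.

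Cost: a sentence or two and one labelled extra model. The primary estimate will include any part of the effect that runs through glucose, so it does not by itself test the hypothesis of a benefit independent of HbA1c.

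**Optional.** Constrain the week-0 means to be equal across arms, or adjust for the baseline outcome, using the coding the plan already describes: "In the event that TIME is modeled using indicator variables, two indicator variables will be used to represent the three time points". Cost: the reported estimate becomes the week-12 difference instead of the slope difference, and the gain may be negligible if a large random slope is kept.

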APPENDIX A: OPTIONAL URINE EXOSOME STUDY

A urine sample is already required as a part of [name] protocol. This urine will be used for urine pregnancy tests (if applicable), and labcorp tests for microalbumin/creatinine ratio. There will likely be excess urine.

Subjects will have the option to opt in or out of a research study in which the urine will undergo a urine exosome analysis.

Purpose of this Study: Exosomes are cell-derived vesicles that are present in many and perhaps all biological fluids, including blood, urine, and cultured medium of cell cultures. The reported diameter of **exosomes** is between 30 and 100 nm, which is larger than LDL, but much smaller than for example, red blood cells. Exosomes are either released from the cell when multivesicular bodies fuse with the plasma membrane or they are released directly from the plasma membrane.^[3] Evidence is accumulating that exosomes have specialized functions and play a key role in, for example, coagulation, intercellular signaling, and waste management.^[1] Consequently, there is a growing interest in the clinical applications of exosomes. Exosomes can potentially be used for prognosis, therapy, and biomarkers for health and disease. In this study we are particularly interested

in exosomes released from podocytes as a marker of podocyte function and podocyte inflammation. Podocytes are often considered a modified endothelium and one of its more commonly used parameter is microalbuminuria. In this study we are using urine exosomes as an added parameter of kidney function other than microalbuminuria and GFR calculation.

The procedure for this study is as follows:

From this sample, 10-20 mL of the fresh spot urine (or as much as possible) is placed into a urine cup containing 1 tab of cOmplete Ultra - protease inhibitor cocktail (Roche) for exosome analysis. The specimen can be refrigerated at 4°C for ~ 1 week or frozen at -80°C until assay, or will be processed for exosomes as follows;

Spot urine for exosomes isolation has been successfully employed in our laboratories from ~15 ml urine using a differential centrifugation method^{2,3}. The supernatant will be subjected to ultracentrifugation, with final centrifugation at 200,000g for 2 hr at 4°C to obtain the urinary exosome pellet. The pellet will be tested for exosomes markers, namely CD63, CD9, CD81, Hsp70, and WT-1, nephrin and podocalyxin, using one of two methods. Preferably mRNA will be extracted and then RT-PCR will be run. Alternative analysis will be done using gel electrophoresis followed by Western blot techniques.

Method 1: Urine exosome mRNA extraction

mRNA extraction from exosomes will be accomplished by using commercial kits (Norgen Biotek Corp., Catalog # 47200). Thereafter, a pre-amplification step will take place, this is a necessary step to measure mRNA in exosomes and will be followed by quantification of specific endothelium and podocyte proteins such as CD9, WT-1, nephrin and podocalyxin by RT-PCR.

Total urinary protein content, albumin and creatinine will be measured via Lapcorp for the same urine samples that have been collected.

Method 2: Gel electrophoresis and Western blot

Exosome pellet will be dissolved in Laemli buffer and proteins will be resolved by gel electrophoresis (4-12% polyacrylamide gel) under denaturing conditions. Subsequently, proteins will be transferred to a PVDF membrane by Western blotting using a dry blotting method (iBlot). The blot will be incubated with blocking solution for 1h, and subsequently exposed to a solution with the first antibody overnight, at 4°C. After washing (5 x 5 min), the membrane will be exposed to a secondary antibody (horseradish peroxidase [HRP]-conjugated) for 1h at room temperature. Finally, the membrane will be incubated with an HRP substrate reagent to reveal the proteins bound to the antibodies tested. Quantitative analysis will be performed by densitometry readings of the positive signals corrected to creatinine concentration of the urine aliquot equivalent to each exosome sample.

End-point: Exploratory but in conjunction with urine albumin/creatinine ratio will help to establish impact of Linagliptin on renal function in diabetes related CKD population.

Guidance document for Adverse Events of Special Interest

Adverse events of special interest are events that we are keeping under close surveillance and we would be very grateful if non-serious adverse events relating to the following medical topics can be reported using the SAE form so that the Global Pharmacovigilance Team receives it as soon as possible:

**Hepatic adverse events
Renal adverse events
Hypersensitivity reactions
Skin lesions
Pancreatitis
Pancreatic cancer
Thyroid neoplasia or cancer
Cardiac failure**

The following information is key in assisting case evaluation. If possible please provide the following when reporting an Adverse Event of Special Interest:

Hepatic adverse events

- Alcohol intake (e.g. grams or units per week) present and past
- Jaundice (personal or family history)
- Hepatobiliary gallstone disease
- Known hepatic disease- eg metabolic, autoimmune, malignancy or - metastatic disease
- Metabolic-induced liver disease, non-alcoholic steatohepatitis (NASH)
- Recent administration of other drugs with known hepatic toxicity- please state reason if these are not recorded as co-suspect drugs
- Environmental exposure to liver toxins (e.g. CCL₄, death cap mushroom, vinyl chloride)
- Substance abuse/Intoxications/Intravenous drug use
- History of drug allergy/hypersensitivity reaction
- Infectious diseases:
 - Bacterial, Protozoic/parasitic hepatic infection
 - Viral hepatic serology
- Travel history
- Blood transfusions history
- Site, radiation and character of pain
- Biopsy results &/or hepatology consult reports
- Radiological investigations eg sonography

Renal adverse events

- Clarity on whether the patient has pre-renal, renal-renal or post-renal failure and the cause of this, eg hypovolaemia due to diarrhoea, glomerulonephritis or bladder obstruction
- Fluid balance if possible
- Baseline renal function and past history of renal insufficiency
- Renal and bladder stone disease- if possible with type of stone (eg Ca oxalate, etc)
- Site, radiation and character of pain
- Biopsy results &/or nephrology consult reports
- Known renal or urinary tract disease
- All BUN / U&Es results
- All urine investigation results including microscopy and culture
- Creatinine clearance
- Radiological investigation reports, eg Kidney-Ureter-Bladder X-ray, Intravenous pyelogram

Hypersensitivity reactions

- Clarity on whether the patient has a diagnosed condition- eg angioedema or anaphylaxis as opposed to reporting symptom of tongue swelling
- For systemic hypersensitivity syndromes, all laboratory and radiological investigations and differential diagnoses
- Clear description of clinical presentation, time course and treatments
- If there are consults from other specialities, please include a copy of the report if possible

Skin lesions

- Clarity on whether the patient has a diagnosed condition as opposed to reporting symptoms
- If a dermatology consult has occurred, please send a copy of the report
- Results of any biopsies
- Estimate of the percentage of the total body surface area that is involved
- Clearly state whether or not there is mouth ulceration
- Clearly state whether or not the rash has blisters
- Please provide any evidence of systemic reaction, laboratory abnormalities

Pancreatitis

- Pancreatic enzymes and liver enzyme values, if possible on presentation and during course of the event
- Baseline and current lipid investigations
- Report of Radiological diagnostic procedures, eg sonography, CT, ERCP
- Clinical symptoms with description of site radiation and character of pain
- Clarity on the diagnosis in the verbatim reported term- eg whether the patient had clinical pancreatitis or asymptomatic enzyme rise
- Permission to contact treating physician for follow up information
- All relevant abnormalities in the pancreaticobiliary tree, eg gallstones, stenosis, CBD thickening
- Alcohol intake

- Clarity on whether the patient has chronic pancreatitis with a known aetiology

Pancreatic cancer

- Please clearly state the start date of the study drug, the start date of the presenting symptoms and the date of diagnosis of cancer
- Please state method of diagnosis, staging, grading and (if available) histology
- Family history of cancer or pancreatitis
- BMI of the patient
- If previous radiology had not shown abnormalities, please confirm if vascular imaging techniques had been requested
- Please state all previous diabetic medication
- Has the patient had previous chemo/radiotherapy? If so please provide details
- Please provide permission to contact pancreatic oncologist

Thyroid neoplasia or cancer

- Please clearly state the start date of the study drug, the start date of the presenting symptoms and the date of diagnosis of cancer
- Please state method of diagnosis, staging, grading and (if available) histology
- Family history of cancer
- Please state all previous diabetic medication
- Has the patient had previous chemo/radiotherapy? If so please provide details
